3.6 Risks and benefits

Secukinumab has shown either preliminary or confirmed efficacy in several inflammatory diseases. The safety profile of secukinumab is primarily based on the aggregate safety data from 10 large completed phase II/III psoriasis trials. The evaluation of safety data from completed PsA trials did not show additional safety concerns.

Secukinumab was generally safe and well-tolerated. The most frequently reported adverse events (AE) are infections, especially upper respiratory tract with secukinumab relative to placebo. There was an increase in mucosal or cutaneous candidiasis with secukinumab compared to placebo, but the cases were generally mild or moderate in severity, non-serious, and responsive to standard treatment.

There was a small increase in mild neutropenia cases with secukinumab compared to placebo. Common Toxicity Criteria (CTC) AE grade 3 neutropenia ($<1.0-0.5 \times 10^9/L$) was uncommonly observed with secukinumab, most were transient and reversible without a temporal relationship to serious infections.

Hypersensitivity reactions include urticarial and rare event of anaphylactic reaction to secukinumab were also observed in clinical studies.

Taking into account the individual risks as outlined above, the expected risk profile of secukinumab from a mechanism of action perspective is anticipated to be similar or improved compared to the approved inflammatory cytokine-targeting therapies. The risk to subjects in this trial will be minimized by compliance with the eligibility criteria, close clinical monitoring and extensive guidance to the investigators, provided in the current version of the IB.

From the standpoint of the overall risk-benefit assessment, current trial with secukinumab is justified.

4 Population

The study population will be comprised of the subjects who have passed screening assessments and comply with eligibility criteria.

Subjects can be re-screened only once and no re-screening study related procedures should be performed prior to written re-consent by the subject. Mis-randomized subjects will not be re-screened.

This is an international study and it is expected that approximately 990 subjects will be randomized.

A screening failure rate of 20% and post-randomization dropout rate of 25% is anticipated in the first year. Enrollment will stop as soon as the target number and proportions of randomized subjects in the respective treatment group is reached.

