Subjects who discontinue study treatment before the end of the trial, hands/wrists and feet X-rays will be taken at the time of study treatment discontinuation. However, if the radiograph performed at time of early discontinuation of study treatment is less than 60 days from a prior X-ray, it does not need to be performed except for Week 16 non-responders where a 30 day time period will apply between Weeks 16 and 24. Likewise, if a scheduled X-ray at Week 24, 52, or 104 is scheduled less than 60 days after any prior hands/wrists and feet X-rays, it does not need to be performed, except for Week 16 non-responders where a 30-day time period will apply between weeks 16 and 24..

The readings of the X-rays and the scoring will be performed centrally. Complete X-ray procedures will be defined in an Imaging Manual provided to the centers by an Imaging CRO designated by Novartis.

[figure not shown]

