9.7 Sample size calculation

A 5% two-sided type I error rate will be used to control for type I error. Three secukinumab regimens will be tested versus placebo with respect to the primary endpoint (ACR20 response), thus the type-I-error will be split to 1.67% two-sided for each comparison. Sample sizes will be based on this type I error assumption. With an assumed placebo rate of 15% and secukinumab 51% (FUTURE 2), the study is over 99% powered to detect a treatment difference of ACR20 in the FAS population, assuming 220 subjects in a secukinumab treatment group, and 330 subjects in the placebo group (Fisher's exact test, nQuery 7.0). This power is applicable for all three dose regimens, as the sample size is driven by structural endpoint.

Power for secondary variables was calculated using a two-sided 1.67% type I error. With an assumed placebo rate of 7% and secukinumab 35% (FUTURE 2), the study is over 99% powered to detect a treatment difference of ACR50 in the full FAS population, assuming 220 subjects in a secukinumab treatment group, and 330 subjects in the placebo group (Fisher's exact test, nQuery 7.0).

For structural endpoint, historical data (FUTURE 1) showed a standard deviation of 1.132 on active treatment and 2.435 on placebo at Week 24, and a difference of 0.52. Using the above

assumptions, there is 83% power to show statistically significant differences assuming 220 subjects in a secukinumab group and 330 subjects in the placebo group (Satterthwaite t-test, nQuery 7.0).

A standard deviation of approximately 0.49 and a treatment difference of 0.17 has been observed for the change from baseline at Week 24 in HAQ-DI[®] (FUTURE 2). Using those assumptions, the study has approximately 94% power to detect a difference between secukinumab and placebo (Two group t-test, nQuery Advisor 7.0), assuming 220 subjects in a secukinumab treatment group and 330 subjects in the placebo group.

For the presence of dactylitis in the subset of subject who have dactylitis at BSL, with an assumed placebo rate of 85% and secukinumab 50% (FUTURE 2), there is about 99% power to show statistically significant difference between secukinumab (110) and placebo (165 subjects), assuming 50% subject have dactylitis at BSL (Fisher's exact test, nQuery 7.0).

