#### **Joint/bone structural damage (vdH-mTSS)**

[figure not shown]
The change at Week 24 from BSL van der Heijde modified Total Sharp Score (vdH-mTSS) will be evaluated using a non-parametric ANCOVA model with treatment regimen and randomization stratum (TNF $\alpha$  status – naïve or IR) as factors, and weight and BSL van der Heijde total modified Sharp score as covariates.

For subjects either on placebo or active, who have a missing vdH-mTSS score at Week 24, linear extrapolation will be used to impute the value at Week 24 if baseline and Week 16 assessments exist. For details about the derivation of the change from baseline see [Section 2.12.4.1](#).

For placebo subjects who meet the criteria for early escape at Week 16, they will be treated as missing for placebo treatment and linear extrapolation will be used to impute the value at Week 24. If BSL or all post- BSL vdH-mTSS values is/are missing for a subject, the subject will be excluded from the analyses.

[figure not shown]
Thus the primary estimand obtained is the difference in the vdH-mTSS scores (secukinumab dose – placebo) at week 24 in the FAS population with at least one baseline and post-baseline vdH-mTSS assessment that would be observed if the possibility for early escape at week 16 were not available to the placebo patient and patients with missing week 24 assessments experienced the same rate of disease progression as up to week 16.

[figure not shown]

- In addition the binary endpoint of no structural progression will be analysed to assess robustness of the results obtained with the primary estimand of the vdH-mTSS. After applying the linear extrapolation as described above no structural progression is defined as those subjects who have a change in vdH-mTSS at Week 24 relative to baseline  $\leq 0.5$ . The proportion of subjects without disease progression at Week 24 will be evaluated using a logistic regression model with treatment group and randomization strata (TNF $\alpha$  status – naïve or IR) as factors, weight and baseline vdH-mTSS as covariates.

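### The 83% power for mTSS is computed correctly but assumes that all 220 and 330 randomised subjects contribute a change score; under the plan's own film and exclusion rules it is about 81%, and about 77% at worst

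*Protocol*

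**What the plan says.** Protocol 9.7, repeated in SAP section 3, takes from an earlier trial "a standard deviation of 1.132 on active treatment and 2.435 on placebo at Week 24" "and a difference of 0.52", and concludes that "there is 83% power to show statistically significant differences assuming 220 subjects in a secukinumab group and 330 subjects in the placebo group" by a Satterthwaite t-test. On the level, 9.7 says "thus the type-I-error will be split to 1.67% two-sided for each comparison" and "Power for secondary variables was calculated using a two-sided 1.67% type I error". It also says that the structural endpoint drives the sample size. Protocol 5.2 randomises 220 subjects to each of three active arms and 165 to each of two placebo arms (3 x 220 + 2 x 165 = 990), so the power calculation uses the randomised numbers unreduced.

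Elsewhere the plan expects fewer evaluable subjects:

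- Protocol section 4 says that a "post-randomization dropout rate of 25% is anticipated in the first year". Section 6 says that withdrawn subjects are not replaced.
- Protocol 6.4.2 plans a film when study treatment is discontinued, but if that film "is less than 60 days from a prior X-ray, it does not need to be performed". A 30-day limit applies instead to Week 16 non-responders between Weeks 16 and 24.
- SAP 2.6.2.2 states: "If BSL or all post- BSL vdH-mTSS values is/are missing for a subject, the subject will be excluded from the analyses". Protocol 9.5.1 has the same rule. The SAP's mTSS estimand is likewise limited to subjects with a baseline and a post-baseline score.
- Only Week 16 non-responders have a scheduled Week 16 film (Table 6-1). SAP 2.6.2.2 extrapolates to Week 24 when baseline and Week 16 films exist; Protocol 9.5.1 asks only for two assessments before Week 24, baseline included.

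**The concern.** Binary endpoints such as ACR20 impute non-response, so the full randomised number is the right denominator for them. mTSS is different: a subject without a post-baseline score leaves the analysis. Where an endpoint is analysed in a subset, the sample-size sections do reduce n (110 and 165 for dactylitis and PASI, 132 and 198 for enthesitis). The mTSS analysis set is also a subset of those randomised, but its n was not reduced.

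This matters most for mTSS. Every other power in the protocol's sample-size section is about 94% or higher, so a few per cent of loss would not be noticed there. mTSS starts at 83%. Its three hypotheses (H4 to H6) also belong to the first family, and all of H1 to H6 must be rejected before any second-family hypothesis is tested. A shortfall on mTSS therefore affects the chance of reaching every later claim.

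**Working it through.** **Inputs from Protocol 9.7.** SD 1.132 (active) and 2.435 (placebo); difference 0.52; two-sided alpha 0.05/3 = 1.67%; n = 220 and 330.

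**Step 1: reproduce the stated figure.**

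- Variance terms: 1.132²/220 = 0.005825 and 2.435²/330 = 0.017967.
- SE = √(0.005825 + 0.017967) = 0.1542.
- Satterthwaite df = (v1 + v2)² / [v1²/(n1 − 1) + v2²/(n2 − 1)] = 498, where v1 and v2 are the two variance terms.
- Critical t = 2.402; noncentrality = 0.52/0.1542 = 3.37.
- Power from the noncentral t = **83.3%**, which matches the stated 83%. Two-sided 5% would give 92.0%, so the plan did use 1.67%.

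There is little slack. The smallest numbers in the 2:3 ratio that still give 83% are about 219 and 329.

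**Step 2: range of loss.** The documents give a first-year dropout rate but no evaluable fraction at Week 24, so the loss L is an assumption. With a constant rate, the share leaving by day t is L = 1 − 0.75^(t/364).

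- *Plan's film rules:* everyone leaving after about Day 60 supplies a usable film, and those leaving earlier do not. L = 1 − 0.75^(60/364) = 4.6%. A straight-line spread gives 0.25 × 60/364 = 4.1%.
- *Worst case at this dropout rate:* nobody leaving before Week 24 (Day 168) supplies a usable film. L = 1 − 0.75^(168/364) = 12.4%. A straight-line spread gives 0.25 × 168/364 = 11.5%.

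**Step 3: power at 220(1 − L) and 330(1 − L), other inputs unchanged.**

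| Loss L | n active | n placebo | Power |
|---|---|---|---|
| 0% | 220 | 330 | 83.3% |
| 4.1% | 210.9 | 316.4 | 81.5% |
| 4.6% | 209.8 | 314.7 | 81.3% |
| 7.3% | 204 | 306 | 80.0% |
| 11.5% | 194.6 | 291.9 | 77.8% |
| 12.4% | 192.6 | 289.0 | 77.4% |

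**Step 4: what decides the position in the range.** The 81% case needs discontinuation films taken between Day 60 and Week 24 to enter the analysis. Under the protocol's extrapolation rule they do. Under the SAP's wording (baseline and Week 16), a film from another time counts only if the visit windows map it to Week 16 or Week 24. SAP 4.1 re-aligns all visits and starts the first window at Day 2, which suggests that an early film would map to the first X-ray window, but the window table is not visible in the text available here. A Week 16 responder with neither a Week 24 nor a discontinuation film has baseline only and is excluded under either rule.

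**The case against.** The strongest reply is that nothing is miscalculated. The sentence is explicitly conditional on 220 and 330, and under that condition it is right. This stands: the point is a missing allowance, not an arithmetic error.

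The second reply is that 25% is study dropout over a year, not film loss at Week 24, and that the plan works to recover films. It schedules one at discontinuation, asks sites to make every effort to obtain scheduled X-rays even from subjects who will not return for the other assessments (Protocol 5.5.9), brings Period 1 discontinuers back for the Week 24 assessments four weeks after the last dose, and extrapolates. This also stands, and it is why about 81% is the leading figure and about 77% only a bound. A reader might be tempted to apply the full 25% and quote 69.7%. The documents do not support that: the rate covers 52 weeks, the endpoint is at Week 24, and many who leave will have a film.

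The third reply is that other features could offset the loss. The planned analysis adjusts for baseline score, weight and stratum. If these correlated 0.2 with change, power at 4.6% loss would be about 83%; at 0.3, about 85%. Level passed on in the graphical procedure could also help: if an mTSS test reached 2.5%, power at 4.6% loss would be about 85%. But the plan states neither correlation, the testing figure is not shown so that path cannot be confirmed, and the printed power claims neither gain.

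Finally, the drop is within planning uncertainty. A placebo SD 5% higher gives 80.1%, 5% lower gives 86.4%, and a difference of 0.50 gives 79.9%. True, but those are unknowns about the disease. The evaluable number follows from the plan's own dropout rate and exclusion rules.

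**Conclusion.** The stated 83% is the power for a trial in which every randomised subject has an evaluable mTSS change, and the plan's own rules do not lead to that trial. Under its film rules the shortfall is about 2 points (power about 81%). At worst it is about 6 points (about 77%), and power drops below 80% once loss exceeds about 7%.

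This rests on four assumptions: the 25% runs evenly over the year, loss is equal across arms, the historical SDs and difference hold, and the t-test calculation is a fair guide to the planned non-parametric ANCOVA. The last was not tested here.

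A reader might infer that the trial is too small or that its tests are compromised. The documents do not support either. At the leading estimate power stays above 80%, and no test, estimand or decision rule is affected. What needs correcting is a stated power on the endpoint said to drive the sample size.

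**What to change.** In Protocol 9.7 and SAP section 3, state the fraction of randomised subjects assumed to have an evaluable mTSS change at Week 24, and restate the power for that number. If the sponsor adopts the assumption that only those leaving before about Day 60 lack a post-baseline film, the figure is about 81%, with a sensitivity range of about 77-81%. If the sponsor has film-retention data from its earlier trials, that fraction should be used and its source named.

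The cost is a sentence or two in each document and a slightly less favourable stated power. No extra enrolment, film or change of analysis is proposed.

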10.1 Regulatory and ethical compliance

This clinical study was designed and shall be implemented and reported in accordance with the ICH Harmonized Tripartite Guidelines for GCP, with applicable local regulations (including European Directive 2001/20/EC, US CFR 21, and Japanese Ministry of Health, Labor, and Welfare), and with the ethical principles laid down in the Declaration of Helsinki.

10.2 Informed consent procedures

Eligible subjects may only be included in the study after providing written (witnessed, where required by law or regulation), Institutional Review Board/Independent Ethics Committee

(IRB/IEC)-approved informed consent, or, if incapable of doing so, after such consent has been provided by a legally acceptable representative of the subject. In cases where the subject's representative gives consent, the subject should be informed about the study to the extent possible given his/her understanding. If the subject is capable of doing so, he/she should indicate assent by personally signing and dating the written informed consent document or a separate assent form. Informed consent must be obtained before conducting any study-specific procedures (i.e. all of the procedures described in the protocol). The process of obtaining informed consent should be documented in the subject source documents.

Novartis will provide to investigators in a separate document a proposed informed consent form that complies with the ICH GCP guideline and regulatory requirements and is considered appropriate for this study. Any changes to the proposed consent form suggested by the investigator must be agreed to by Novartis before submission to the IRB/IEC, and a copy of the approved version must be provided to the Novartis monitor after IRB/IEC approval.

Women of child bearing potential should be informed that taking the study treatment may involve unknown risks to the fetus if pregnancy were to occur during the study and agree that in order to participate in the study they must adhere to the contraception requirement for the duration of the study, and for minimum 16 weeks or longer if local label requires it (e.g. 20 weeks in EU) after the last dose. If there is any question that the subject will not reliably comply, they should not be entered in the study.

10.3 Responsibilities of the investigator and IRB/IEC

Before initiating a trial, the investigator/institution should obtain approval/favorable opinion from the IRB/IEC for the trial protocol, written informed consent form, consent form updates, subject recruitment procedures (e.g., advertisements) and any other written information to be provided to subjects. Prior to study start, the investigator is required to sign a protocol signature page confirming his/her agreement to conduct the study in accordance with these documents and all of the instructions and procedures found in this protocol and to give access to all relevant data and records to Novartis monitors, auditors, Novartis Quality Assurance representatives, designated agents of Novartis, IRBs/IECs, and regulatory authorities as required. If an inspection of the clinical site is requested by a regulatory authority, the investigator must inform Novartis immediately that this request has been made.

10.4 Publication of study protocol and results

Novartis assures that the key design elements of this protocol will be posted in a publicly accessible database such as clinicaltrials.gov. In addition, upon study completion and finalization of the study report, the results of this trial will be either submitted for publication and/or posted in a publicly accessible database of clinical trial results.

11 Protocol adherence

This protocol defines the study objectives, the study procedures and the data to be collected on study participants. Additional assessments required to ensure safety of subjects should be administered as deemed necessary on a case by case basis. Under no circumstances should an investigator collect additional data or conduct any additional procedures for any research related purpose involving any investigational drugs.

Investigators ascertain they will apply due diligence to avoid protocol deviations. If an investigator feels a protocol deviation would improve the conduct of the study this must be considered a protocol amendment, and unless such an amendment is agreed upon by Novartis and approved by the IRB/IEC it cannot be implemented. All significant protocol deviations will be recorded and reported in the CSR.

To meet the Classification of Psoriatic Arthritis (CASPAR) criteria for diagnosis of psoriatic arthritis according to ([Taylor 2006](#)), a subject must have inflammatory articular disease (joint, spine or enthesal) and at least 3 points from the following 5 categories:

1. Evidence of current psoriasis, a personal history of psoriasis, or a family history of psoriasis
 - Current psoriasis is defined as psoriatic skin or scalp disease present today as judged by a rheumatologist or dermatologist.* **(2 points)**
 - A personal history of psoriasis is defined as a history of psoriasis that may be obtained from a patient, family physician, dermatologist, rheumatologist, or other qualified health care provider. **(1 points)**
 - A family history of psoriasis is defined as a history of psoriasis in a first- or second-degree relative according to patient report. **(1 points)**
2. Typical psoriatic nail dystrophy including onycholysis, pitting, and hyperkeratosis observed on current physical examination **(1 point)**
3. A negative test result for the presence of rheumatoid factor by any method except latex **(1 point)**
4. Either current dactylitis, defined as swelling of an entire digit, or a history of dactylitis recorded by a rheumatologist **(1 point)**
5. Radiographic evidence of juxta-articular new bone formation appearing as ill-defined ossification near joint margins (but excluding osteophyte formation) on plain radiographs of the hand or foot **(1 point)**

Total score:

(The CASPAR criteria eCRF will autopopulate the total number of points of the CASPAR criteria met by the subject. If the total score ≥ 3 , the subject meets CASPAR criteria for PsA diagnosis.)

* Current psoriasis is assigned a score of 2; all other features are assigned a score of 1

14 **Appendix 2: Guidelines for administering the questionnaires for patient reported outcomes**

Before trial start

Study coordinators should familiarize themselves with the PRO questionnaire(s) in the trial and identify any items where a patient's response might highlight issues of potential concern.

At BSL, BSA involvement with psoriasis should be determined before completing PRO questionnaire(s) to ensure that DLQI is completed only for patients who have BSA \geq 3%.

For example, one question in the SF-36 asks 'How much of the time in the past 4 weeks- have you felt downhearted and blue?' If a patient responds 'most or all of the time', then the study coordinator should inform the study investigator.

Before completion

1. Subjects should be provided with the correct questionnaire at the appropriate visits and in the appropriate language
2. Subjects should have adequate space and time to complete the forms
3. Patients should be provided with a firm writing surface (such as a table or a clip board)
4. Questionnaire should be administered before the clinical examination

During completion

1. Administrator may clarify the questions but should not influence the response
2. Only one response for each question
3. Also see "Addressing Problems and Concerns"

After completion

1. Check for completeness and not for content*
2. Data should be sent from the eCRF / electronic device
3. Data should be reviewed by Investigator for AEs

*However, any response which may directly impact or reflect the patient's medical condition (e.g. noting of depression) should be communicated by the study coordinator to the investigator).

Addressing Problems and Concerns

Occasionally a patient may have concerns or questions about the questionnaires administered. Guidance related to some of the most common concerns and questions are given below.

The patient does not want to complete the questionnaire(s)

Tell the patient that completion of the questionnaire(s) is voluntary. The goal is to better understand the physical, mental and social health problems of patients. Emphasize that such information is as important as any other medical information and that the questionnaire(s) is simple to complete. Suggest that the questionnaire(s) may be different from anything the

respondent has filled in the past. If the patient still declines, retrieve the questionnaires. Record the reason for the decline and thank the patient.

The patient is too ill or weak to complete the questionnaire(s)

In these instances, the coordinator may obtain patient responses by reading out loud each question, followed by the corresponding response categories, and entering the patient's response. No help should be provided to the patient by any person other than the designated study coordinator. The coordinator should not influence patient responses. The study coordinator cannot translate the question into simpler language and has to be read verbatim.

The patient wants someone else to complete the questionnaire(s)

In no case should the coordinator or anyone other than the patient provide responses to the questions. Unless specified in the study protocol, proxy data are *not* an acceptable substitute for patient self-report. Patients should be discouraged from asking a family member or friend for help in completing a questionnaire.

The patient does not want to finish completing the questionnaire(s)

If non-completion is a result of the patient having trouble understanding particular items, ask the patient to explain the difficulty. Re-read the question for them *verbatim* but do not rephrase the question. If the respondent is still unable to complete the questionnaire, accept it as incomplete. Thank the patient.

The patient is concerned that someone will look at his/her responses

Emphasize that all responses are to be kept confidential. Point out that their names do not appear anywhere on the questionnaire, so that their results will be linked with an ID number and not their name. Tell the patient that his/her answers will be pooled with other patients' answers and that they will be analyzed as a group rather than as individuals. Tell the patient that completed forms are not routinely shared with treating staff and that their responses will only be seen by you (to check for completeness) and by the investigator. Any response which may directly impact on or reflect their medical condition (*e.g.* noting of severe depression) will be communicated by the coordinator to the physician.

The patient asks the meaning of a question/item

While completing the questionnaire, some patients might ask the meaning of specific items so that they can better understand and respond. If this happens, assist the patient by rereading the question for them *verbatim*. If the patient asks to interpret the meaning of an item, do not try to explain it, but suggest that he/she use his/her own interpretation of the question. Patients should answer the questions based on what *they* think the questions mean.

A General Information about all questionnaire(s):

All questionnaires have to be completed by the patients in their local languages using an electronic device. The questionnaires should be completed by the patients in a quiet area free from disturbance, and before any visit assessments. Patients should receive no help from family members; if questions cannot be answered alone (due to problems with reading or

understanding), then the doctor or nurse should read the questions and record the patient's responses without influencing their answers. The information provided is strictly confidential and will be treated as such. If a patient has missed a question or given more than one response per question, then this should be brought to patient. Incomplete questions should not be accepted without first encouraging the patient to complete unanswered questions.

The investigator must complete the patient/visit information on the electronic device and ensure that the center number, patient's number and initials are identical to the CRF. As there are no source data for this questionnaire, the data queries will be restricted to patient/visit information.

15 Appendix 3: American College of Rheumatology (ACR) Measures and Criteria of Response

Number of tender joints

Seventy-eight joints (78) are scored as either tender or not tender: 8 distal interphalangeal, 10 proximal interphalangeal, 10 metacarpophalangeal and 2 first carpometacarpal joints of the hands, 8 distal interphalangeal, the 10 metatarsophalangeal and 10 proximal interphalangeal joints of the feet, the 2 wrists, 2 elbows, 2 shoulders, 2 acromioclavicular, 2 sternoclavicular, 2 temporomandibular, 2 hip, 2 knee, 2 talo-tibial, and 2 mid-tarsal joints.

Joint tenderness is to be scored present (1) or absent (0).

Number of swollen joints

Joints are to be scored as either swollen (1) or not swollen (0). The 76 joints to be examined for swelling are the same as those examined for tenderness, however excluding both hip joints.

Patient's assessment of PsA pain

On a 100 mm non-anchored visual analog scale, from no pain to unbearable pain.

Patient's global assessment of disease activity

On a 100 mm non-anchored visual analog scale, from no arthritis activity to maximal arthritis activity, after the question "Considering all the ways your arthritis affects you, draw a line on the scale for how well you are doing".

Physician's global assessment of disease activity

On a 100 mm non-anchored visual analog scale, from no arthritis activity to maximal arthritis activity.

Patient's assessment of physical function

Health Assessment Questionnaire – HAQ-DI[©]ACR20/50/70*

A patient will be considered as improved according the ACR20 criteria* if she/he has at least 20% improvement in

- the two following measures:
 - Tender joint count
 - Swollen joint count
- and at least 3 of the following 5 measures:
 - Patient's assessment of pain
 - Patient's global assessment of disease activity
 - Physician's global assessment of disease activity
 - Health Assessment Questionnaire (HAQ[©]) score
 - C-reactive protein (CRP)/Erythrocyte Sedimentation Rate (ESR).

ACR50 = 50% improvement in at least 3 of the 5 measures and 50% improvement in the swollen and tender joint count.

ACR70 = 70% improvement in at least 3 of the 5 measures and 70% improvement in the swollen and tender joint count.

Reference: ([Felson et al 1995](#))

17 Appendix 5: The Psoriasis Area and Severity Index (PASI)

The PASI is a system used for assessing and grading the severity of psoriatic lesions and their response to therapy. The PASI produces a numeric score that can range from 0 to 72. The severity of disease is calculated as follows. In the PASI system, the body is divided into 4 regions: the head (h), trunk (t), upper extremities (u), and lower extremities (l), which account for 10%, 30%, 20% and 40% of the total BSA, respectively. Each of these areas is assessed separately for erythema, induration and desquamation (scaling), which are each rated on a scale of 0 to 4. The scoring system for the signs of the disease (erythema, induration, and desquamation (scaling)) are:

0 = none; 1 = slight; 2 = moderate; 3 = severe; and 4 = very severe.

The scale for estimating the area of involvement for psoriatic lesions is outlined below.

0 = no involvement

1 = 1% to 9% involvement

2 = 10% to 29% involvement

3 = 30% to 49% involvement

4 = 50% to 69% involvement

5 = 70% to 89% involvement

6 = 90% to 100% involvement

To help with the area assessments, the following conventions should be noted:

- the neck is considered part of the head
- the axillae and groin are part of the trunk
- the buttocks are part of the lower extremities

The PASI formula is: $PASI = 0.1(Eh + Ih + Dh)Ah + 0.3(Et + It + Dt)At + 0.2(Eu + Iu + Du)Au + 0.4(El + Il + Dl)Al$ (where E = erythema, I = induration, D = desquamation and A = area)

Table 17-1 PASI Scoring Worksheet

| | Head | Upper extremities | Trunk | Lower extremities |
|---|------------------------|------------------------|------------------------|------------------------|
| 1. Redness † | | | | |
| 2. Thickness † | | | | |
| 3. Scale † | | | | |
| 4. Sum of rows 1, 2, and 3 | | | | |
| 5. Area score ‡ | | | | |
| 6. Score of row 4 x row 5 x the area multiplier | Row 4 x row 5 x 0.1 | Row 4 x row 5 x 0.2 | Row 4 x row 5 x 0.3 | Row 4 x row 5 x 0.4 |
| 7. Sum row 6 for each column for PASI score | | | | |
| a. Divide body into four areas: head, arms, trunk to groin, and legs to top of buttocks. | | | | |
| b. Generate an average score for the erythema, thickness, and scale for each of the 4 areas (0=clear, 1-4=increasing severity). | | | | |
| c. Sum scores of erythema, thickness, and scale for each of the 4 area. | | | | |

[figure not shown]
- d. Generate a percentage for skin covered with psoriasis for each area and convert that to a 0-6 scale. ‡
- e. Multiply score of item c above times item d above for each area and multiply that by 0.1, 0.2, 0.3 and 0.4 for head, arms, trunk, and legs, respectively.
- f. Add these scores to get the PASI score.

† Erythema, thickness, and scale are measured on a 0-4 scale (none, slight, mild, moderate, severe)

‡ Area scoring criteria (score: % involvement).

- 0: 0% (clear)
- 1: <10%
- 2: 10-<30%
- 3: 30-<50%
- 4: 50-<70%
- 5: 70-<90%
- 6: 90-100%

Derived from [Feldman and Krueger, 2005](#). Psoriasis assessment tool in clinical trials. Ann Rheum Dis; 64;ii65-ii68.

19 Appendix 7: Liver event and Laboratory trigger Definitions and Follow-up Requirements

Table 19-1 Liver Event and Laboratory Trigger Definitions

| Definition/ threshold | |
|-----------------------|---|
| LIVER | 3 x ULN < ALT / AST \leq 5 x ULN |
| LABORATORY TRIGGERS | 1.5 x ULN < TBL \leq 2 x ULN |
| LIVER EVENTS | ALT or AST > 5 x ULN ALP > 2 x ULN (in the absence of known bone pathology) TBL > 2 x ULN (in the absence of known Gilbert syndrome) ALT or AST > 3 x ULN and INR > 1.5 Potential Hy's Law cases (defined as ALT or AST > 3 x ULN and TBL > 2 x ULN [mainly conjugated fraction] without notable increase in ALP to > 2 x ULN) Any clinical event of jaundice (or equivalent term) ALT or AST > 3 x ULN accompanied by (general) malaise, fatigue, abdominal pain, nausea, or vomiting, or rash with eosinophilia Any adverse event potentially indicative of a liver toxicity * |

* These events cover the following: hepatic failure, fibrosis and cirrhosis, and other liver damage-related conditions; non-infectious hepatitis; benign, malignant and unspecified liver neoplasms

TBL: total bilirubin; ULN: upper limit of normal

Table 19-2 Follow Up Requirements for Liver Events and Laboratory Triggers

| Criteria | Actions required | Follow-up monitoring |
|--------------------------------------|---|--|
| Potential Hy's Law case ^a | Discontinue the study drug immediately Hospitalize, if clinically appropriate Establish causality Complete liver eCRF | ALT, AST, TBL, Alb, PT/INR, ALP and γ GT until resolution ^c (frequency at investigator discretion) |
| ALT or AST | | |
| > 8 x ULN | Discontinue the study drug immediately Hospitalize if clinically appropriate Establish causality Complete liver eCRF | ALT, AST, TBL, Alb, PT/INR, ALP and γ GT until resolution ^c (frequency at investigator discretion) |
| > 3 x ULN and INR > 1.5 | Discontinue the study drug immediately Hospitalize, if clinically appropriate Establish causality Complete liver eCRF | ALT, AST, TBL, Alb, PT/INR, ALP and γ GT until resolution ^c (frequency at investigator discretion) |
| > 5 to \leq 8 x ULN | Repeat LFT within 48 hours If elevation persists, continue follow-up monitoring If elevation persists for more than 2 weeks , discontinue the study drug Establish causality Complete liver eCRF | ALT, AST, TBL, Alb, PT/INR, ALP and γ GT until resolution ^c (frequency at investigator discretion) |

| Criteria | Actions required | Follow-up monitoring |
|--|--|--|
| > 3 × ULN accompanied by symptoms ^b | Discontinue the study drug immediately Hospitalize if clinically appropriate Establish causality Complete liver eCRF | ALT, AST, TBL, Alb, PT/INR, ALP and γGT until resolution ^c (frequency at investigator discretion) |
| > 3 to ≤ 5 × ULN (patient is asymptomatic) | Repeat LFT within the next week If elevation is confirmed, initiate close observation of the patient | Investigator discretion Monitor LFT within 1 to 4 weeks |
| ALP (isolated) | | |
| > 2 × ULN (in the absence of known bone pathology) | Repeat LFT within 48 hours If elevation persists, establish causality Complete liver eCRF | Investigator discretion Monitor LFT within 1 to 4 weeks or at next visit |
| TBL (isolated) | | |
| > 2 × ULN (in the absence of known Gilbert syndrome) | Repeat LFT within 48 hours If elevation persists, discontinue the study drug immediately Hospitalize if clinically appropriate Establish causality Complete liver eCRF | ALT, AST, TBL, Alb, PT/INR, ALP and γGT until resolution ^c (frequency at investigator discretion) Test for hemolysis (e.g., reticulocytes, haptoglobin, unconjugated [indirect] bilirubin) |
